5.4 Student Outcome Measures

Parent, teacher, and student measures will be collected at pre-treatment and post-treatment of the pilot trial to assess changes in mental health symptoms and academic engagement.

Mental health symptoms. The BASC-3 ⁵⁵ is a 138-item, 4-point, Likert-type rating scale for assessing parental report of child mental health functioning, standardized for ages 2.5 to 18 years. The BASC-3 has excellent psychometric properties. ⁵⁵ The BASC-3 (*Aggression, Conduct Problems, and Anxiety* scales) will be administered at pre- and post-treatment for children who participate in CPP, CATS or CICO. Parents will complete the paper and pencil version of the BASC-3⁵⁵ over the phone with a research assistant or they may complete electronically. When this measure is administered to Spanish proficient parents, the research assistant will call language services to connect to an interpreter and the measure will be completed by phone.

Student academic engagement. The Engagement versus Disaffection with Learning: Teacher Report (EvsD) ⁷¹ will be completed by teachers for all children receiving Tier 2 interventions. This is a 20-item, four-point instrument with four sub-scales: (a) *Behavioral Engagement*, (b) *Emotional Engagement*, (c) *Behavioral Disaffection*, and (d) *Emotional Disaffection*. The survey will be completed by hand or electronically via REDCap survey. We will use the average score for each of the four scales at pre- and post-participation in CPP, CATS or CICO.

Externalizing and Internalizing Problems: Children will complete The Behavior and Feeling Survey-Your Report (YFS-SR). The YFS-SR is a brief (10 items) measure of internalizing and externalizing problems rated on a 5-point scale. The YFS-SR has excellent psychometric properties and it is sensitive to change. ⁵⁰ The YFS-SR provides three scores (Internalizing, Externalizing, Total). The measure will be completed at pre- and post-treatment for children who participate in group CBT or CICO.

5.5 Remote Training Strategy Feedback

Perception of Training Support. Qualitative Interview. We will conduct semi-structured qualitative interviews with BHS and administrators in each condition. These interviews will be audio-recorded and conducted over the phone or via Webex and should last approximately 30 minutes in length. Teachers will not be interviewed. We will seek to interview one administrator at each school. We will utilize purposive sampling with BHS,

focused on variation in interventions implemented and levels of experience. In interviews with administrators, we will utilize an interview guide designed to understand existing Tier 2 programs at their school as well as their perceptions of the training support's feasibility, acceptability, appropriateness, and usability. In interviews with BHS, we will utilize an interview guide that seeks to elicit views and perspectives about the perceived feasibility, acceptability, appropriateness, and usability of the training support they received. The audio recorded interviews will be transcribed by ADA transcription services. We will conduct a thematic analysis of these data and compare across conditions.

6 STATISTICAL CONSIDERATIONS

The statistical analysis plan (SAP) will be updated and finalized before the data base lock. The SAP will provide comprehensive descriptive information of the statistical analysis plan, including approaches for summarizing primary and secondary endpoints at baseline and post treatment. All statistical analyses will be performed using SAS®, 73version 9.4 or higher

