3.2 Study Duration, Enrollment and Number of Sites

Behavioral Health Staff: BHS will be asked to commit to participate in the study for one school year. The school the BHS works at will be randomly selected as a participating school for either years 1,2, or 3 of the study. BHS will be free to implement the EBPs outside the research project after their participation in the study has concluded.

Students: Students who are eligible, based on the SDQ, SCARED, and SAEBRS, and for whom consent/assent is obtained, will participate in the study for the time it takes them to receive one of the interventions. Participation includes receiving interventions consisting of CI/CO, CPP, or CATS. The interventions will consist of one 40-minute/class period intervention session conducted at school or two brief daily check-ins also conducted during the school day. Post-treatment data will be collected by a parent/caregiver and teacher using the BASC-3 and Engagement versus Disaffection with Learning Teacher Report (EvsD-Teacher). Students will be asked to complete the Behavior and Feelings Survey.

Administrators: School principals and/or administrators will be asked to complete a qualitative interview about their experience with the project.. The interview will occur at the end of the academic year and their participation will last the time it takes to complete the interview

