4.3.1 Remote Consultation for Remote Video plus Coaching

BHS will receive a study-purchased audio recorder to use to record the student groups. They will be instructed to upload the recording to OneDrive. Research team consultants will provide synchronous consultation to BHS in the RV+ condition via Webex. The consultation will have two main components: (a) session preparation (CPP/CATS) or review and planning (CICO) and (b) coaching.

Session Preparation: Session preparation for CPP and CATS will consist of (a) discussing referrals to the groups; (b) conducting a step-by-step walkthrough of the session objectives, (c) reviewing the CBT principles behind the treatment components for that session; (d) encouraging adherence and the use of active learning strategies; (e) problem-solving barriers to implementation and helping implementers reflect on past challenges (e.g., attendance problems, organizational barriers, materials/resources) in order to successfully implement the next session with appropriate adaptations as needed; and (f) enhancing BHS's use of empathy and positive reinforcement through modeling. Research consultants for CICO will (a) review the school's CICO implementation manual and (b) provide feedback and suggestions for program implementation.

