The CI/CO IGFC/Quality Measure, or part 2 of the IGFC/Content Measure, is also completed by the consultant (research staff) once teams submit their completed CI/CO Implementation Guide. The IGFC/Quality Measure is a 14-item measure of the quality of, or degree to which, team responses in customizing their respective CI/CO Implementation Guides are comprehensive, clear, feasible. Measurement entails examining team responses to items related to the (a) implementation roles and responsibilities, (b) implementation process, (c) motivation system, (d) fading and self-monitoring, (e) training/orientation of staff, mentors, students and families, and (f) data entry and progress monitoring. The IGFC/Quality Measure will be scored by recording a score of 0-3 for each item depending on whether or not the team response meets the criteria for being comprehensive, clear, and feasible (with 1 point awarded for each).

Process Fidelity to CI/CO. Process fidelity for CI/CO will be assessed with the Check-In/Check-Out Fidelity Checklist, a measure of the daily implementation of CI/CO. The CI/CO Fidelity Checklist is completed by the consultant (research staff) on a monthly basis after collecting the completed Daily Progress Report (DPR) student forms for each student involved in CICO. The Check-in/Check-Out Fidelity Checklist is an 11-item form that indicates whether or not students received daily CICO feedback based on the occurrence of the following: (a) student identification, (b) feedback date, (c) recorded goal, (d) behavioral expectations rated by the teacher for each period, (e) the number of daily points earned out of the number of possible points, (f) an indication of whether or not the goal was met, and (g) the signature of the teacher/mentor. The 11 items will be scored as "occurred" or "did not occur." The Check-In/Check-Out Fidelity Checklist will be scored by recording occurrence over occurrence-plus-non-occurrence and multiplying the decimal by 100.

Adoption Inventory (AI). The AI will track the number of times each intervention is used per school, per condition. This information will be collected one time at the end of the intervention via a REDCap survey.

Dosage Inventory (DI). The DI is an Excel tracking sheet exported from the website hosting the video modules listing the number of times and length of time each video module is accessed by BHS.

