6.3 Statistical Methods

Data will be analyzed using an intent-to-treat approach, wherein each participant (BHS or student) will be kept in the arm to which the school was randomized, regardless of treatment

received. In addition to creating pre/post change scores and analyzing the data using t-tests (or the Wilcoxon signed rank test), a mixed-effects model will be explored for analyzing the pre/post repeated-measures endpoints related to student academic engagement and mental health symptoms. A student-level random effect will be included and modeled using the unstructured covariance matrix to account for within-subject dependence due to repeated measurements. The models will include study arm (RTS or CC) and time of measurement (pre/post) as fixed effect. Arm x Time interaction effects will be included in the model as well. This modeling approach will allow us to compare pre-to-post changes and the extent to which these changes differ across study arms. For the purpose of generating statistical estimates for an anticipated phase 3 larger scale study, the nested nature of students within the school as well as BHS within the school will be explored using a hierarchical mixed effect multilevel model. Furthermore, we will explore marginal models using generalized estimating equations (GEE; ^{74,75}), which will produce robust estimates that adjust for clustering at the school level. Although SAS PROC MIXED will not remove participants with post-missing data from the analysis, missing data will be kept to a minimum. As a sensitivity analysis, we will impute the potential missing data using the maximum likelihood method for imputation. ⁷⁶

For the mixed-methods analyses (survey and semi-structured interview data about perceived appropriateness, feasibility, and acceptability of the training and consultation procedures, and BHS's opinions about the support they received), we will use the same data analytical approach described in IRB Protocol # 20-017895.

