8.2 Data Collection and Management

The data collection and management plan is consistent with CHOP Policy A-3-6: Acceptable Use of Technology Resources that defines the requirements for encryption and security of computer systems.

- Identifiable data will be collected as part of this study. This data includes full names/initials, date of birth, address, telephone number, e-mail addresses. However, participants will be identified by alphanumeric code only. This precautionary step allows for the electronic transfer of data without using data encryption techniques. At each stage of data collection and maintenance, measures are taken to ensure that all identifying information is taken out of data archives, and any hard copies of data that could identify participants are stored in locked file cabinets with restricted access, and that data files are password protected. Participant identification numbers are used that do not reveal the identity of participants (e.g., no use of birth dates, initials, social security numbers, etc.). Only members of the research team will have access to the data. If the results of this study are presented at scientific meetings or published in professional journals, they will not contain information that could be used to identify BHS, or parents/students.
 - Hard data will be kept in locked file cabinets at the Roberts Center for Pediatric Research. Audio recordings (containing participant identifiers) will also be stored in locked file cabinets at CHOP. The files will be transferred and stored to a CHOP computer network drive and analyzed by study team members for the coding of integrity/fidelity scoring. After all analyses are complete, the files will be maintained for 6 years in accordance with CHOP policy A-3-9, then be destroyed and personal identifiers will not be retained with the data. All computerized study databases for questionnaire data will be kept on a secure Windows NT server located at one of the hospital's research buildings. This server is also protected by a firewall to reduce the risk of unauthorized access to study information.
 - Remote data collection will only take place via secure video chat platforms and/or the telephone. Study team members will record the data onto paper CRFs in the
-

same manner as in-person data collection, and no digital video or audio recordings will be created.

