- Data collected as part of this study will be entered (data entry from CRFs or upload from Excel files) and stored using REDCap (Research Electronic Data Capture) database, a secure web-based software database supporting clinical and translational research databases. The database will be password-protected, stored, and backed up on a daily basis by CHOP's Research Institute. REDCap provides data management functionality; including automated export procedures for seamless data downloads to Excel and commonly used statistical packages (SPSS, SAS, Stata, R). The database will incorporate range checks and between-variables consistency checks to ensure quality control. The system will signal the presence of questionable or potentially incorrect items. After data cleaning and quality assurance procedures are completed, pertinent sets of data will be converted into SAS format for statistical analysis. The Biostatistics and Data Management Core (BDMC) of the Research Institute will provide staff expertise in REDCap database design and implementation, randomization, and statistical analysis under the direction of the study's biostatistician.

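### The SAP may be updated until database lock in a trial with no described masking and no named primary model, so the main analysis could be settled with outcomes in view

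*Combined protocol and SAP*

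**What the plan says.** **Timing.** Section 6 sets one deadline: "The statistical analysis plan (SAP) will be updated and finalized before the data base lock". Nothing ties the SAP to a cohort or to the first outcome data.

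**Staggered entry.** Under section 3.2 each school "will be randomly selected as a participating school for either years 1,2, or 3 of the study", so outcomes from earlier cohorts will exist before a final lock.

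**Who knows the arm, and who scores.** Section 4.3.1: "Research team consultants will provide synchronous consultation to BHS in the RV+ condition via Webex". Section 5.3: "The CI/CO Fidelity Checklist is completed by the consultant (research staff) on a monthly basis". Fidelity is a primary endpoint (section 6.1). No masking of raters, investigators or statistician is described.

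**Access.** Section 8.2: "Only members of the research team will have access to the data". No limit by arm is given. The same section says the biostatistics core "will provide staff expertise in REDCap database design and implementation, randomization, and statistical analysis".

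**Open analyses.** Section 6.3 offers t-tests on change scores or a Wilcoxon test, and then "a mixed-effects model will be explored for analyzing the pre/post repeated-measures endpoints". A hierarchical model and GEE are also to be explored. Section 6.2 adds ANCOVA if a baseline measure differs significantly, and transformation where needed, without a criterion. None of these is called primary. Section 6.1 lists at least nine primary endpoints: content and process fidelity, three BASC-3 scales and four engagement scales.

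**The concern.** Finalising a SAP before lock protects a trial mainly when nobody can see outcomes by arm until then. That condition is not established here. If the model is chosen once outcomes by arm could be known, the choice can follow the results, even without intent. Reported effects then drift towards the more favourable candidate, and a reader cannot verify which analysis was prespecified. This is an estimation pilot, so the damage would fall mainly on the effect sizes and intervals used to plan the larger study, not on a confirmatory claim.

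**Working it through.** **1. The plan's own precision figures.** Section 6.4 gives margins of 9.3 (content fidelity, SD 16, 24 per arm), 0.35 (process fidelity, SD 0.6, 24 per arm) and 2.4 (student change, SD 8, 89 per arm). The formula is half-width = t(0.975, 2n−2) × SD × √(2/n).

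- Content fidelity: 2.013 × 16 × √(2/24) = 9.30
- Process fidelity: 2.013 × 0.6 × √(2/24) = 0.349
- Student change: 1.974 × 8 × √(2/89) = 2.37

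All three reproduce. They match an unclustered two-sample t-test, which is only one of the analyses left open.

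**2. How far the interval depends on the model.** With 89/8 = 11.125 students per school, the design effect is 1 + 10.125 × ICC. The documents give no ICC, so 0 to 0.10 is assumed. With 8 schools per arm (14 degrees of freedom, t = 2.145), the student half-width is 2.145 × 8 × √(2/89 × design effect).

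- ICC 0.05: design effect 1.506, half-width 3.16
- ICC 0.10: design effect 2.013, half-width 3.65

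So whether the main model accounts for school moves the interval from 2.37 to between 3.16 and 3.65.

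**3. Selection among analyses, without clustering.** Simulated trials had no true effect, 89 students per arm, one endpoint and one contrast (100,000 runs; Monte Carlo error at most about 0.09 points). The pre/post correlation is assumed. Rank-sum stands for the Wilcoxon option because the groups are independent. In the conditional column, ANCOVA is used only when baseline differs at p < 0.05; otherwise t-test or rank-sum is chosen freely.

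| Correlation | Any one test | Free choice of three | ANCOVA conditional |
|---|---|---|---|
| 0.5 | 4.9–5.0% | 8.1% | 5.2% |
| 0.68 | 4.9–5.0% | 7.6% | 5.4% |
| 0.8 | 4.9–5.0% | 7.2% | 5.6% |

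**4. With clustering.** A second null simulation (4,000 runs, 8 schools per arm, 11 students per school, correlation 0.5) took the best of five: the same three tests, a school-mean analysis standing in for the hierarchical model, and GEE with a normal reference.

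| ICC | Best of five | Change-score t-test alone | School-mean alone | GEE alone |
|---|---|---|---|---|
| 0 | 11.9% | 5.4% | 5.2% | 9.2% |
| 0.05 | 18.1% | 11.2% | 5.0% | 8.9% |
| 0.10 | 23.6% | 16.6% | 5.3% | 8.7% |

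Most of the best-of-five rate at ICC 0.05 and 0.10 is already present in the unclustered t-test on its own. The 11.9% at ICC 0 owes much to GEE without a small-sample correction. These rows mainly measure ignored clustering and too few schools. They are not the size of the timing problem.

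**The case against.** Finalising before lock is ordinary practice, and no interim or by-arm look is planned. A reader might infer that arm-level results will be visible, or that one person randomizes, manages and analyses the data. The documents support neither. Monthly scoring by a consultant is stated only for check-in/check-out process fidelity. The content checklist for that intervention is completed once. Group-session fidelity is scored by coders whose timing and role in coaching are not given. The BASC-3 and engagement scales are reported by parents and teachers. A consultant who sees one school's checklist has not seen a comparison of arms. Section 8.2 names a core that supplies several services, not a single individual. All of this stands, and it limits the point to what the rule permits.

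The rival analyses are also fewer than they look. With two time points, complete data and an unstructured covariance, the arm-by-time test is the same as the change-score t-test. The hierarchical model has a stated planning purpose. ANCOVA is conditional, and following that condition removes most of the excess. This stands too, and the size is reported accordingly.

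Finally, section 6.4 says the pilot is meant to estimate effects and is not sized for hypothesis tests, so to speak of a deciding analysis would overstate it. However, sections 6.2 and 6.3 still plan between-group comparisons, and the estimates are intended for a phase 3 study. No bias in the effect size has been computed, only false-positive rates.

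**Conclusion.** The point holds as a weakness in a stated rule. The SAP can change until lock, no masking is described, earlier cohorts will have outcomes by then, and no primary model is named. Selection is possible, not shown. The lack of masking is inferred from the roles described and from silence elsewhere.

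For one endpoint and one contrast without clustering, the false-positive rate is 7.2–8.1% under free choice of three tests, but 5.2–5.6% under the plan's own conditional ANCOVA rule. Both ranges assume a pre/post correlation of 0.5 to 0.8 and normal data. They do not count the nine or more endpoints or the two comparisons with control. A reader might take the 12–24% from the clustered simulation as the cost of late finalisation. That reading fails, because most of the excess at ICC 0.05–0.10 comes from leaving out the school and the rate at ICC 0 owes much to uncorrected GEE. The practical stake is the credibility of the estimates and intervals passed to the larger trial. The change is worth making because it costs almost nothing.

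**What to change.** Replace the sentence in section 6 with: *The SAP will be finalised, dated and archived before post-treatment or fidelity data from the first cohort are released for analysis; later changes will be dated and reported as post hoc.* The trigger should be release for analysis. A trigger of summarising by arm would already be met by the present rule if nobody summarises early.

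In the SAP, for each primary endpoint, make one model that accounts for school the main analysis, and always adjust for the baseline score where one exists. Keep the t-test or Wilcoxon test, the student-only mixed model and GEE as sensitivity analyses. Have the programs written on coded arm labels. If first-cohort data by arm have already been seen, disclose this and finalise now.

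Cost: no change to sample size or data collection. The work is one sentence, a named model for at least nine endpoints, and a data set with coded arms. The downside is that later improvements must be labelled post hoc. The change does not stop a consultant from seeing the checklists that he or she scores. It fixes the analysis before those scores reach the analyst.

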6.1 Primary and SecondaryEndpoints

The primary endpoints related to school staff implementing the interventions are measures of content and process fidelity. Primary endpoints related to student outcomes are pre-to-post changes in student mental health symptoms (measured by Behavior Assessment System for Children- 3rd Edition (BASC-3),⁵⁵ which include Aggression, Conduct Problems, Anxiety, and Academic engagement measured by Behavioral Engagement, Emotional Engagement, Behavioral Disaffection and Emotional Disaffection.

Secondary endpoints are: the mediators and moderators effects of consultation support on behavioral health staff fidelity and the qualitative examination of school staff's perceived feasibility, appropriateness and acceptability of the support they received.

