An increasing number of schools in rural settings are employing the multi-tier positive behavioral interventions and supports (PBIS) framework to improve school-climate. PBIS can also be used as a framework for the adoption and integration of evidence-based practices (EBPs) for children's mental health concerns. A key challenge is that school personnel need technical assistance (training plus ongoing consultation) in order to implement EBPs with fidelity. In urban and suburban schools, this support can be provided to school staff on site. However, providing ongoing on-site support is not feasible or sustainable in the majority of rural schools, due to their remote physical location. For this reason, video technology has been recommended for the training of behavioral health staff (BHS) in under-served rural communities.

Objectives:

The purpose of this study is to test the effectiveness of a remote training platform with BHS in schools serving rural communities.

Study Design:

This study is a pilot randomized controlled trial to compare implementation and student outcomes of three training strategies: Control Condition (CC), Remote Video (RV), and Remote Video plus Coaching (RV+).

Setting/Participants:

Participants will be school personnel with and without prior mental health training and students in grades 4-8 in schools serving rural communities who are deemed at risk for externalizing and internalizing mental health disorders. The pilot trial will be conducted in 24 schools (8 in CC, 8 in RV, and 8 in RV+). It is estimated that a total of 72 behavioral health staff (3 staff per school- 24 per arm) and 312 students (13 students per school - 104 per arm) will participate in this study. Additionally, we estimate about 24 school administrators such as principals or assistant principals will approve school's participation.

Study Interventions and Measures:

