2.2 Secondary Objectives (or Aim)

The secondary objectives are the evaluation of implementation and student outcomes.

- To explore mediators and moderators of consultation support on behavioral health staff fidelity.
- To qualitatively examine school staff's perceived feasibility, appropriateness and acceptability of the support they received.

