5.3 Implementation Fidelity

Content Fidelity to Tier 2 Group CBT (CPP & CATS). The Content Fidelity Checklist (CFC) reflects each activity component of the session agenda of the treatment protocols. Raters use a yes/no response scale to indicate whether or not the implementer covered a particular component. All GCBT sessions will be audio-recorded. 100% of sessions will be

coded by the first coder and approximately 20% of sessions will be randomly selected and coded by the second coder. Interrater reliability will be evaluated using Kappa coefficients⁶⁹

Process Fidelity to Tier 2 Group CBT (CPP & CATS). Process fidelity will be assessed via an adapted version of the rating system developed by Lochman and colleagues.⁷⁰ Ten items are rated on a scale of 0 to 4, with 0 being "Not At All" and 4 being "Very Often". Ratings are given on the extent to which school staff members delivered the intervention in an orderly fashion, using active learning strategies, etc. Exploratory factor analysis (EFA) yielded two factors on the 10-item scale. We will use the average *Total* and factor scores for analysis. 100% of sessions will be coded by the first coder and approximately 20% of sessions will be coded by the second coder. Interrater reliability will be evaluated using ICC.

Content Fidelity for CI/CO. Content fidelity for CI/CO will be assessed via the CI/CO Implementation Guide Fidelity Checklist (IGFC). The CI/CO IGFC is completed by the consultant (research staff) after school teams submit their completed CI/CO Implementation Guide. The IGFC is completed once and measures both the content and quality of the customized manual components for each school. The CI/CO IGFC/Content Measure is a 26-item measure of CI/CO customization of the following CI/CO components: (a) staff roles and responsibilities, (b) CI/CO process logistics, (c) daily progress report, (d) motivation system, (e) fading and self-monitoring procedures, (f) staff training procedures, and (g) data collection and progress monitoring procedures. Each item is scored according to completion status as "yes," "no," or "not applicable." The CI/CO IGFC/Content Measure will be scored by recording the frequency of "yes" scores over the frequency of "yes," and "no" scores.

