6.4 Sample Size and Power

The proposed pilot study aims to collect data and estimate effect sizes measuring the effect of RV and RV+ when compared to the CC. Although, this pilot study is not powered to test for specific hypotheses regarding effect sizes, the sample size estimates were based on data obtained from our recently completely NIH funded study, ^{15,77} we estimated that a total of 72 BHS (24 per arm) and 312 students will participate in this study. With 24 BHS per arm, a two-sided 95% confidence interval in mean differences in content fidelity (CF) and process fidelity (PF between) RV or RV+ vs. CC will be produced. The minimum distance from the mean difference to the limits (margins of error) will equal to 9.3 (CF) and 0.35 (PF) with the estimated pooled standard deviations equal to 16 and 0.6 respectively. It is anticipated that 104 students per arm will be recruited (total = 312). Assuming a uniform attrition rate of 15%, a total of 268 evaluable students will be included in the final statistical analysis. With 89 students in each of the three study arms, a two-sided 95% confidence interval for mean differences in pre/post changes in student mental health symptoms and academic engagement between the two arms ((RV or RV+) vs. CC) will equal to 2.4 with estimated

pooled standard deviation equal to 8. Sample size justification was reported using PASS 13 software.⁷⁸

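### At least nine scores share primary status in Section 6.1, with inconsistent arm contrasts, no deciding comparison and no error control, while Section 2.2 calls the same outcomes secondary

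*Combined protocol and SAP*

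**What the plan says.** **Endpoints.** Section 6.1 has two groups of primary endpoints. For staff, "The primary endpoints related to school staff implementing the interventions are measures of content and process fidelity". For students, "Primary endpoints related to student outcomes are pre-to-post changes in student mental health symptoms", "which include Aggression, Conduct Problems, Anxiety, and Academic engagement", the last through four engagement scales. Section 5.4 scores those four separately, with no composite. Section 5.3 uses different fidelity instruments for the group programmes and for CI/CO, and for group process fidelity it adds: "We will use the average *Total* and factor scores for analysis".

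**Objectives.** Section 2.1 gives the primary objective as a comparison of three training strategies and names no outcome. Section 2.2 then says: "The secondary objectives are the evaluation of implementation and student outcomes".

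**Contrasts.** Section 6.4 compares RV or RV+ with CC. Section 6.2 announces a comparison among all three groups, then speaks of two. Section 6.3 gives the model an arm term with two levels, RTS or CC; RTS is not in the abbreviation list.

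**Testing or estimation.** The abstract says: "The purpose of this study is to test the effectiveness of a remote training platform with BHS in schools serving rural communities". Section 6.3 says: "In addition to creating pre/post change scores and analyzing the data using t-tests (or the Wilcoxon signed rank test), a mixed-effects model will be explored". Section 6.4 says that the aim is to estimate effect sizes and that "this pilot study is not powered to test for specific hypotheses regarding effect sizes". The documents state no test significance level, lead endpoint, hierarchy, alpha split or success rule.

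**The concern.** The plan does not say which result would answer the trial's question. Nine or more scores have the same rank, the arms can be compared in several ways, and Sections 2.2 and 6.1 disagree on whether these outcomes are primary at all. The candidates can easily point in different directions: fidelity may improve while symptoms do not, or RV+ may differ from CC while RV does not. As written, whichever comparison falls below 0.05 could be reported as a primary finding that the training is effective.

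An estimation aim does not remove the problem. Section 6.3 says that estimates from this pilot will inform a larger phase 3 study. If the most favourable of many estimates is carried forward because it was the one that stood out, it will tend to overstate the true effect.

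**Working it through.** **1. The plan's own figures.** Section 6.4 gives half-widths of two-sided 95% confidence intervals. Formula: t(0.975, 2n − 2) × SD × √(2/n).

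- Content fidelity, n = 24 per arm, SD 16: 2.013 × 16 × √(2/24) = 9.30 (stated 9.3).
- Process fidelity, n = 24 per arm, SD 0.6: 2.013 × 0.6 × √(2/24) = 0.349 (stated 0.35).
- Student change, n = 89 per arm, SD 8: 1.974 × 8 × √(2/89) = 2.37 (stated 2.4).

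All three reproduce with no multiplicity allowance. That is normal for interval-width sizing and is not an error. It shows only that error control has not been built in elsewhere.

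**2. Counting endpoints (Section 6.1).** 2 fidelity + 3 BASC-3 + 4 engagement = 9. The student scales alone are 3 + 4 = 7.

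**3. Counting contrasts.**

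| Reading | Source | Contrasts | Tests, 9 endpoints | Tests, 7 endpoints |
|---|---|---|---|---|
| RV and RV+ pooled vs CC | two-level term, 6.3 | 1 | 9 | 7 |
| RV vs CC, RV+ vs CC | 6.4 | 2 | 18 | 14 |
| Adding RV+ vs RV | three groups, 6.2 | 3 | 27 | 21 |

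**4. Chance of at least one false-positive result.** Assumptions that are not in the documents: each test is two-sided at 0.05 (only implied by the 95% intervals), there is no true effect on any endpoint, and all endpoints share one common correlation r. Three equal arms were simulated as normal scores. Each pairwise difference was divided by √2, and the pooled contrast (mean of RV and RV+ minus CC) by √1.5. The trial counts as positive if any absolute value exceeds 1.96. The dependence created by the shared arms is therefore included.

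| Endpoints | r | 1 contrast | 2 contrasts | 3 contrasts |
|---|---|---|---|---|
| 9 | 0 | 37% | 58% | 69% |
| 9 | 0.5 | 27% | 44% | 54% |
| 9 | 0.8 | 17% | 28% | 35% |
| 7 (student) | 0 | 30% | 49% | 60% |
| 7 (student) | 0.5 | 23% | 38% | 47% |
| 7 (student) | 0.8 | 15% | 26% | 32% |

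Check at r = 0 with one contrast: 1 − 0.95⁹ = 0.370 and 1 − 0.95⁷ = 0.302, which match.

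**5. Contrasts alone.** One endpoint with no contrast singled out gives about 9% (two contrasts) or 12% (three), so naming an endpoint without naming a contrast would not be enough.

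**The case against.** The strongest reply is that this is a pilot. Section 6.4 says it estimates effects, disclaims power for specific hypotheses and justifies the sample size by interval width. A trial of that kind need not control family-wise error. That stands, and it rules out reading the point as a failed confirmatory test. It does not dispose of the point, because the abstract twice describes the study as a test of effectiveness and Section 6.3 prescribes tests on change scores.

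Three stronger readings are tempting, and the documents do not support them:

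- **A single rate, such as 44–54%, stated as fact.** Those figures are two and three contrasts at r = 0.5. The documents give no correlation and no test alpha, and the pooled reading in 6.3 gives 27% at the same r. RV+ vs RV is inferred from 6.2; Section 6.4 names only contrasts with CC.
- **Significance tests on all nine endpoints.** The test sentence in 6.3 concerns pre/post change. Fidelity has no pre-training score, and for it 6.4 gives only interval widths. The seven-scale rows are the firmer ones.
- **About 14 primary endpoints.** Counting each fidelity score in 5.3 gives 7, plus 7 student scales. But 6.1 does not name the factor scores as primary, and a Total overlaps with its own factors.

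The single common correlation is also crude, since staff fidelity and student change are measured on different units. This is a reason to quote a range.

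Section 6 says that the SAP will be updated and finalised before database lock. This makes the change timely, but the section does not promise a multiplicity rule.

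**Conclusion.** The point holds as a defect of definition that should be corrected before the SAP is finalised. At least nine scores have equal primary status, Sections 2.2 and 6.1 contradict each other, the arm comparison has three incompatible descriptions, and nothing says which result decides or how error is controlled.

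The size is conditional on the assumptions in the working. Over correlations of 0.8 to 0, every reading is well above 5%, from about 15% (seven student scales, one pooled contrast) to about 69% (nine endpoints, three contrasts). The structural finding does not depend on where in that range the truth lies. Given Section 6.4, the harm is selective emphasis and an inflated effect passed to phase 3.

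**What to change.** 1. Make 2.2 and 6.1 agree on which outcomes are primary.
2. State the arm contrasts as RV vs CC and RV+ vs CC throughout Section 6, and replace the two-level arm term in 6.3 with the three randomised arms.
3. In 6.1 and 6.3, report all these endpoints as estimates with 95% confidence intervals and no claims of significance or effectiveness.
4. In both places in the abstract, replace the wording about testing effectiveness with estimating effects, in line with 6.4.

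If the sponsor wants to keep a significance claim, it should name in advance one endpoint and one contrast, put any other tests in a fixed order or under Holm adjustment, and report everything else as estimates. The endpoint must name its instrument. Content fidelity alone is not enough, because 5.3 measures it with a session checklist for the groups and with a once-completed implementation-guide checklist for CI/CO.

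The cost is wording only, with no new data or participants. The downside is that most endpoints can no longer support a significance claim.
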